4.6.2. Benefit Assessment

The addition of UMEC to FF/VI in asthma has the potential to improve lung function, reduce moderate/severe exacerbations and improve quality of life in patients whose asthma is inadequately controlled on ICS/LABA alone. Current asthma treatment guidelines recommend the addition of a LAMA (tiotropium) for patients that are uncontrolled on ICS/LABA (GINA 2016 Steps 4 and 5); the availability of the FF/UMEC/VI combination would therefore be consistent with this approach. The combination in a closed triple combination would provide the convenience of once daily dosing and reduce the need for multiple inhalers. Furthermore, the availability of two doses of FF would allow the prescriber to select an appropriate inhaled corticosteroid dose based on the severity of asthma.

4.6.3. Overall Benefit: Risk Conclusion

Taking into account the measures taken to minimize risk to subjects participating in the study, the potential risks identified in association with FF/UMEC/VI are justified by the anticipated benefits that may be afforded to subjects with asthma.

The current experience with FF, UMEC and VI and the lack of significant safety concerns relevant to the asthma population provides reassurance that the potential risks associated with the known pharmacology of these compounds is offset by the potential significant benefits that are afforded to patients inadequately controlled on ICS/LABA therapy.

The ICS/LABAs used as run-in (FSC) and stabilization/comparator arms (FF/VI) are both marketed for the treatment of asthma and have favourable benefit-risk profiles.

5. SELECTION OF STUDY POPULATION AND WITHDRAWAL CRITERIA

Specific information regarding warnings, precautions, contraindications, adverse events, and other pertinent information on the GSK investigational product or other study treatment that may impact subject eligibility is provided in the IB.

Deviations from inclusion and exclusion criteria are not allowed because they can potentially jeopardize the scientific integrity of the study, regulatory acceptability or subject safety. Therefore, adherence to the criteria as specified in the protocol is essential.

In order to confirm eligibility, a review of each subject's medical records must be performed prior to a subject entering the run-in period. To be enrolled into the study, subjects will be required to meet the additional enrolment criteria (see Section 5.3); to be

randomised into the study, subjects will be required to meet the additional randomization criteria (see Section 5.4).

5.1. Inclusion Criteria

A subject will be eligible for inclusion in this study only if all of the following criteria apply:

AGE
1. 18 years of age or older at the time of signing the informed consent.

TYPE OF SUBJECT AND DIAGNOSIS INCLUDING DISEASE SEVERITY

2. Diagnosis: Subjects with a diagnosis of asthma as defined by the National Institutes of Health [NIH 2007] at least one year prior to Visit 0.
 
3. Symptomatic: Subjects with inadequately controlled asthma (ACQ-6 score ≥ 1.5) despite ICS/LABA maintenance therapy at Visit 1.
 
4. Asthma Control: Note: please refer to the SRM for guidance on the following: In the 1 year prior to Visit 1:
 
 • A documented healthcare contact for acute asthma symptoms 
OR
 
 • A documented temporary change in asthma therapy for acute asthma symptoms, according to a pre-specified asthma action plan (or equivalent) 
5. Current Asthma Maintenance Therapy: Subjects are eligible if they have required daily ICS/LABA for at least 12 weeks prior to Visit 0 with no changes to maintenance asthma medications during the 6 weeks immediately prior to Visit 0 (including no changes to a stable total dose of ICS of >250 mcg/day fluticasone propionate [FP, or equivalent]).
 
Examples of acceptable doses of commonly prescribed ICS medication are provided in the GINA guidelines [GINA 2016], [BTS/SIGN 2016], [Japanese guidelines for adult asthma 2017]. Dosing regimen (once or twice daily to equal the total daily dose) should be restricted to the current local product labels/treatment guidelines.
 
6. Spirometry: A best pre-bronchodilator morning (AM) FEV₁ $\geq 30\%$ and $<85\%$ of the predicted normal value at Visit 1. Predicted values will be based upon the European Respiratory Society (ERS) Global Lung Function Initiative [Quanjer 2012].
 
7. Reversibility of Disease: airway reversibility defined as $\geq 12\%$ and ≥ 200 mL increase in FEV₁ between 20 and 60 minutes following 4 inhalations of albuterol/salbutamol aerosol at Visit 1.
 
Note: If the subject does not meet the above reversibility criteria at Visit 1 then the reversibility assessment may be repeated once within 7 days of Visit 1 if either criteria a) or b) are met:

- a) $\geq 9\%$ increase in FEV_1 between 20 and 60 minutes following 4 inhalations of albuterol/salbutamol aerosol at Visit 1.
- b) Documented evidence of a reversibility assessment within 1 year prior to Visit 1 which demonstrated a post-bronchodilator increase in FEV_1 of $\geq 12\%$ and ≥ 200 mL.

Should the subject successfully demonstrate airway reversibility (defined as $\geq 12\%$ and ≥ 200 mL increase in FEV_1 between 20 and 60 minutes following 4 inhalations of albuterol/salbutamol aerosol) at the second attempt then, provided that all other eligibility criteria assessed at Visit 1 are met, the subject may enter the 3-week run-in period (see Section 7.3.4.1).

8. **Short-Acting β_2 Agonists (SABAs):** All subjects must be able to replace their current SABA inhaler with albuterol/salbutamol aerosol inhaler at Visit 1 as needed for the duration of the study. Subjects must be judged capable of withholding albuterol/salbutamol for at least 6 hours prior to study visits.

SEX

9. **Male or Eligible Female**, defined as having documentation of non-reproductive potential or reproductive potential as follows:

A female subject is eligible to participate if she is not pregnant (as confirmed by a negative serum human chorionic gonadotrophin (hCG) test), not lactating, is not planning on becoming pregnant during the study and at least one of the following conditions applies:

- a. Non-reproductive potential defined as:
- Pre-menopausal females with one of the following:
 - Documented tubal ligation
 - Documented hysteroscopic tubal occlusion procedure with follow-up confirmation of bilateral tubal occlusion
 - Hysterectomy
 - Documented Bilateral Oophorectomy
 - Postmenopausal defined as 12 months of spontaneous amenorrhea with an appropriate clinical profile (e.g., age appropriate, >45 years, in the absence of hormone replacement therapy). In questionable cases for women <60 years of age, a blood sample with simultaneous follicle stimulating hormone and estradiol falling into the central laboratory's postmenopausal reference range is confirmatory. Females under 60 years of age, who are on hormone replacement therapy (HRT) and whose menopausal status is in doubt, are required to use a highly effective method to avoid pregnancy if they wish to continue their HRT during the study. Otherwise, they must discontinue HRT to allow confirmation of post-menopausal status prior to study enrolment. For most forms of HRT, at least 2 to 4 weeks will elapse between the cessation of therapy and the blood draw; this interval depends on the type and dosage of HRT. Following

confirmation of their post-menopausal status, subjects can resume use of HRT during the study without use of a highly effective method to avoid pregnancy.

- b. Reproductive potential and agrees to follow one of the options listed in the Modified List of Highly Effective Methods for Avoiding Pregnancy in Females of Reproductive Potential (FRP) (see [Appendix 5](#)) from the screening visit until after the last dose of study medication and completion of the follow-up visit.
- c. The Investigator is responsible for ensuring that subjects understand how to properly use these methods of contraception.

INFORMED CONSENT

10. Informed Consent: Able to give written informed consent prior to participation in the study, which will include the ability to comply with the requirements and restrictions listed in the consent form and in this protocol. Subjects must be able to read, comprehend, and write at a level sufficient to complete study related materials.

5.2. Exclusion Criteria

Deviations from exclusion criteria are not allowed because they can potentially jeopardise the scientific integrity of the study, regulatory acceptability or subject safety. Therefore, adherence to the criteria as specified in the protocol is essential.

A subject will not be eligible for inclusion in this study if any of the following criteria apply:

CONCURRENT CONDITIONS/MEDICAL HISTORY (INCLUDES LIVER FUNCTION AND QTc INTERVAL)

1. **Pneumonia:** Chest X-ray documented pneumonia in the 6 weeks prior to Visit 1.
2. **Asthma Exacerbation:** Any asthma exacerbation requiring a change in maintenance asthma therapy in the 6 weeks prior to Visit 1.

Note: Subjects requiring a temporary change in asthma therapy (e.g., oral corticosteroids or increased dose of ICS) to treat an exacerbation in the 6 weeks prior to Visit 1 are not explicitly excluded at Visit 1 provided that, at the Investigator's discretion, the subject's condition is stable after they have resumed their pre-exacerbation maintenance asthma therapy (without modification) and they are considered appropriate for enrolment into this study of up to 12 months' duration.

3. **Chronic Obstructive Pulmonary Disease:** Subjects with the diagnosis of chronic obstructive pulmonary disease, as per Global Initiative for Chronic Obstructive Lung Disease ([GOLD 2016](#)) guidelines, including all of the following:
 - History of exposure to risk factors (i.e., especially tobacco smoke, occupational dusts and chemicals, smoke from home cooking and heating fuels). For personal tobacco use, see exclusion criterion number 14: [Tobacco Use](#);

AND

- A post-albuterol/salbutamol FEV₁/Forced Vital Capacity (FVC) ratio of <0.70 and a post-albuterol/salbutamol FEV₁ of ≤70% of predicted normal values;

AND

- Onset of disease ≥40 years of age

4. **Concurrent respiratory disorders:** Subjects with current evidence of pneumonia, active tuberculosis, lung cancer, significant bronchiectasis, sarcoidosis, lung fibrosis, pulmonary hypertension, interstitial lung diseases or other active pulmonary diseases or abnormalities other than asthma.
5. **Risk Factors for Pneumonia:** immune suppression (e.g., HIV, Lupus) or other risk factors for pneumonia (e.g., neurological disorders affecting control of the upper airway, such as Parkinson's Disease, Myasthenia Gravis).
Patients at potentially high risk (e.g., very low BMI, severely malnourished, or very low FEV₁) will only be included at the discretion of the Investigator.
6. **Other diseases/abnormalities:** Subjects with historical or current evidence of clinically significant cardiovascular, neurological, psychiatric, renal, hepatic, immunological, gastrointestinal, urogenital, nervous system, musculoskeletal, skin, sensory, endocrine (including uncontrolled diabetes or thyroid disease) or hematological abnormalities that are uncontrolled. Significant is defined as any disease that, in the opinion of the Investigator, would put the safety of the subject at risk through participation, or which would affect the efficacy or safety analysis if the disease/condition exacerbated during the study.
7. **Unstable liver disease** as defined by the presence of ascites, encephalopathy, coagulopathy, hypoalbuminaemia, esophageal or gastric varices or persistent jaundice, cirrhosis, known biliary abnormalities (with the exception of Gilbert's syndrome or asymptomatic gallstones). **Note:** *Chronic stable hepatitis B and C are acceptable if the subject otherwise meets entry criteria*
8. **Clinically significant ECG abnormality:** Evidence of a clinically significant abnormality in the 12-lead ECG performed during screening. The Investigator will determine the clinical significance of each abnormal ECG finding in relation to the subject's medical history and exclude subjects who would be at undue risk by participating in the trial. An abnormal and clinically significant finding is defined as a 12-lead tracing that is interpreted as, but not limited to, any of the following:
 - Atrial Fibrillation (AF) with rapid ventricular rate >120 beats per minute (BPM);
 - Sustained or nonsustained ventricular tachycardia (VT);
 - Second degree heart block Mobitz type II and third degree heart block (unless pacemaker or defibrillator had been inserted);
 - QTcF ≥500 msec in patients with QRS <120 msec and QTcF ≥530 msec in patients with QRS ≥120 msec
9. **Unstable or life threatening cardiac disease:** subjects with any of the following at Screening (Visit 1) would be excluded:
 - Myocardial infarction or unstable angina in the last 6 months
 - Unstable or life threatening cardiac arrhythmia requiring intervention in the

last 3 months

- New York Heart Association (NYHA) Class IV Heart failure [[American Heart Association 2016](#)]

10. **Antimuscarinic effects:** Subjects with a medical condition such as narrow-angle glaucoma, urinary retention, prostatic hypertrophy or bladder neck obstruction should only be included if in the opinion of the Investigator the benefit outweighs the risk and that the condition would not contraindicate study participation.
11. **Cancer:** Subjects with carcinoma that has not been in complete remission for at least 5 years. Subjects who have had carcinoma *in situ* of the cervix, squamous cell carcinoma and basal cell carcinoma of the skin would not be excluded based on the 5 year waiting period if the subject has been considered cured by treatment.
12. **Questionable validity of consent:** Subjects with a history of psychiatric disease, intellectual deficiency, poor motivation or other conditions that will limit the validity of informed consent to participate in the study.

CONCOMITANT MEDICATIONS/TREATMENTS

13. **Medication prior to spirometry:** Subjects who are medically unable to withhold their albuterol/salbutamol for the 6-hour period required prior to spirometry testing at each study visit.

RELEVANT HABITS

14. **Tobacco Use:** Subjects who are:
- Current smokers (defined as subjects who have used inhaled tobacco products within the 12 months prior to Visit 1 [i.e., cigarettes, e-cigarettes/vaping, cigars or pipe tobacco]).
 - Former smokers with a smoking history of ≥ 10 pack years (e.g., ≥ 20 cigarettes/day for 10 years).
- Note: Refer to the SRM for the formula for calculating pack years.*
15. **Drug/alcohol abuse:** Subjects with a known or suspected history of alcohol or drug abuse within the last 2 years.

CONTRAINDICATIONS

16. **Allergy or Hypersensitivity:** A history of allergy or hypersensitivity to any corticosteroid, anticholinergic/muscarinic receptor antagonist, beta₂-agonist, lactose/milk protein or magnesium stearate.

DIAGNOSTIC ASSESSMENTS AND OTHER CRITERIA

17. **Non-compliance:** Subjects at risk of non-compliance, or unable to comply with the study procedures. Any infirmity, disability, or geographic location that would limit compliance for scheduled visits.
18. **Affiliation with Investigator site:** Study Investigators, sub-Investigators, study coordinators, employees of a participating Investigator or study site, or immediate family members of the aforementioned that is involved with this study.

19. **Inability to read:** In the opinion of the Investigator, any subject who is unable to read and/or would not be able to complete study related materials.

5.3. Enrolment Criteria

Those subjects who meet the enrolment criteria will be enrolled into the study until the target of approximately 2250 randomised subjects is reached.

At the end of the run-in period, study subjects must fulfil the following additional criteria in order to be enrolled in the study and enter the 2-week stabilization period:

5.3.1. Inclusion Criteria for Enrolment

TYPE OF SUBJECT AND DIAGNOSIS INCLUDING DISEASE SEVERITY

1. **Inadequately controlled asthma:** Subjects with inadequately controlled asthma (ACQ-6 score ≥ 1.5) at Visit 2.
2. **Percent-predicted FEV₁:** A best pre-bronchodilator morning (AM) FEV₁ $\geq 30\%$ and $< 90\%$ of the predicted normal value at Visit 2. Predicted values will be based upon the ERS Global Lung Function Initiative [[Quanjer 2012](#)].

CONCURRENT CONDITIONS/MEDICAL HISTORY

3. **Liver function tests at Visit 1:**
 - alanine aminotransferase (ALT) $< 2 \times$ upper limit of normal (ULN)
 - alkaline phosphatase $\leq 1.5 \times$ ULN
 - bilirubin $\leq 1.5 \times$ ULN (isolated bilirubin $> 1.5 \times$ ULN is acceptable if bilirubin is fractionated and direct bilirubin $< 35\%$)

eDIARY

4. **Compliance** with completion of the Daily eDiary reporting defined as completion of all questions/assessments on ≥ 4 of the last 7 days during the run-in period.

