9.2. Sample Size Considerations

9.2.1. Sample Size Assumptions

Sample size calculation is based on the primary efficacy endpoint of mean change from baseline in trough FEV₁ at the end of the 24-week treatment period.

A total of 2250 randomized subjects are required for this study, with 375 subjects in each of the six double-blind treatment groups:

- FF/VI 100/25 mcg
- FF/VI 200/25 mcg
- FF/UMEC/VI 100/31.25/25 mcg
- FF/UMEC/VI 200/31.25/25 mcg
- FF/UMEC/VI 100/62.5/25 mcg
- FF/UMEC/VI 200/62.5/25 mcg

Assuming 10% missing data on spirometry at the end of the 24-week treatment period, due to early withdrawal from study, approximately 337 subjects per treatment group should have trough FEV₁ data available for the analysis.

The standard deviation for the mean change from baseline in trough FEV₁ at the end of the 24-week treatment period is estimated to be 400 mL based on previous asthma studies. The proposed sample size of n=337 per treatment group should provide 90% power, assuming a difference of 100 mL, based on a two sample t-test with a two sided significance level of 0.05 for each of the two primary comparisons of interest for each UMEC dose.

For the target population, it is assumed that the mean exacerbation rate is 2 per year for the control group FF/VI; this was based on a review of previous FF/VI asthma exacerbation study conducted by GSK and Tio asthma studies conducted by Boehringer Ingelheim. The proposed sample size of 750 randomized subject per arm (based on the treatment comparison of combined triple therapies and combined dual therapies with both FF doses) should have approximately 95% power if the true reduction in exacerbation

rate for triple therapy vs. dual therapy is 20%. The calculation assumes the number of exacerbations per year follows a negative binomial distribution [Keene 2007], with a dispersion parameter $k=0.7$ based on a previous FF/VI asthma exacerbation study, and assumes the following accelerative recruitment rate per week over a period of 39 weeks:

[figure not shown]
- 3.5 weeks at 15 patients/week
- 4.5 weeks at 25 patients/week
- 4.5 weeks at 35 patients/week
- 4.5 weeks at 45 patients/week
- 4.5 weeks at 55 patients/week
- 4.5 weeks at 70 patients/week
- 13 weeks at 90 patients/week

The duration of the treatment period is variable but will be at least 24 weeks and up to a maximum of 52 weeks, with the end of study date being established once the last subject has been randomized.

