9.4.1. Primary Analyses

The primary efficacy endpoint is the mean change from baseline in trough FEV₁ at the end of the 24-week treatment period. For each subject, the baseline value of clinic FEV₁ is the last acceptable/borderline acceptable (pre-dose) FEV₁ value obtained prior to randomization (either from Visit 3 pre-dose or from Visit 2 pre-bronchodilator).

The primary efficacy analysis will evaluate the “de facto” type estimand in the Intent-to-Treat population, using a mixed-model repeated measures (MMRM) analysis, including all trough FEV₁ recorded post randomization. Analyses will include the fixed, categorical effects of treatment, visit, treatment by visit interaction, sex, randomization stratification by pre-study ICS treatment dosage strength (mid, high) at screening, as well as the continuous, fixed covariates of age, baseline value, and baseline value by visit interaction. Point estimates and 95% confidence intervals will be calculated for the following primary comparisons of interest.

There are two treatment comparisons to demonstrate the replicate efficacy for the UMEC 62.5 mcg dose:

- FF/UMEC/VI 100/62.5/25 mcg vs. FF/VI 100/25 mcg
- FF/UMEC/VI 200/62.5/25 mcg vs. FF/ VI 200/25 mcg

Additionally, there will be two treatment comparisons for the UMEC 31.25 mcg dose to demonstrate the replicate efficacy for the UMEC 31.25 mcg dose:

- FF/UMEC/VI 100/31.25/25 mcg vs. FF/VI 100/25 mcg
- FF/UMEC/VI 200/31.25/25 mcg vs. FF/ VI 200/25 mcg

In addition, a de jure estimand, including data collected over the randomized double-blind treatment period, will be analyzed using a MMRM model. Sensitivity analyses to assess the impact of missing data will be detailed in the RAP.

Other pairwise treatment comparisons of interest as outlined in Section 9.3.3 will also be provided for the primary efficacy endpoint.

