## **6.2. Demographic and Baseline Characteristics**

Each of the following types of data will be summarized:

- Demographic data (age, sex, ethnicity, weight, height, body mass index (BMI))
- Pre-study ICS Dosage at Screening)
- Age ranges (12-17, 18-64,  $\geq 65$ -84,  $\geq 85$ )
- Race and racial combinations, race and racial combination details
- Disease Duration (duration of asthma, onset age (year) of asthma)
- Asthma medical history questionnaire
- History of exacerbations over the previous year (Number of exacerbations in previous year (0,1,  $\geq 2$ ) treated without oral/systemic corticosteroids, treated with oral/systemic corticosteroids, requiring hospitalization, treated with oral/systemic corticosteroids or requiring hospitalization, and total number of exacerbations)
- Smoking history (smoking status of non-smoker or former smoker, and pack years for former smokers)
- Cardiovascular history/risk factors and family history of cardiovascular risk factors.
- Spirometry at Visit 1 and Visit 2: pre- and post-bronchodilator for FEV1, FVC, and FEV1/FVC, reversibility by albuterol/salbutamol at Visit 1 and by ipratropium at Visit 2, and associated percent predicted values. Note: Predicted values will be based upon the European Respiratory Society (ERS) Global Lung Function Initiative [Quanjer, 2012].
- Spirometry at Visit 3: pre-dose FEV1, FVC, FEV1/FVC, and associated percent predicted values.

- Change in pre-bronchodilator / pre-dose FEV1 from Visit 1 to Visit 2 during run-in period, from Visit 2 to Visit 3 during the stabilisation period, and from Visit 1 to Visit 3 during the run-in/stabilisation periods.
- Home spirometry during the three weeks of the run-in period and the two weeks of the stabilisation period.
- FeNO at Visit 3.
- Total serum IgE at Visit 1.
- ACQ-5, ACQ-6, and ACQ-7 scores at Visit 1, Visit 2, and Visit 3.
- Change in ACQ-5, ACQ-6, and ACQ-7 scores from Visit 1 to Visit 2 during run-in period, from Visit 2 to Visit 3 during the stabilisation period, and from Visit 1 to Visit 3 during the run-in/stabilisation periods.
- Summary of past and current medical histories.
- Summary of pneumonia history.

In addition to the tables listed above; demography, race and racial combination details, disease history and history of exacerbations will also be summarized by pooled FF treatment groups.

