**7.1.6. Statistical Methodology Specification**

Primary Statistical Analyses
Endpoint

 
• Mean change from baseline in trough FEV1 at Week 24
 

Primary Model Specification

 
• Mixed Models Repeated Measures (MMRM) model.
 
• The analysis is based on ‘de facto’ type estimand, based on the ITT population.
 
• Clinic trough FEV1 (both on- and post-treatment) data collected prior to and at Week 24 will be included in the analysis.
 
• No imputation is made on missing data.
 

Primary Statistical Analyses

 
• While missing data are not explicitly imputed in the MMRM analyses, there is an underlying assumption that the data are missing at random. All available data will be utilized via modeling of the within-participant correlation structure, the derived treatment differences will be adjusted to take into account the missing data.
 
• Terms in the model: 
 
○ Dependent Variable: change from baseline in trough FEV1 at each visit
 
○ Covariates: 
 
▪ Categorical: treatment group, sex, region, visit, pre-study ICS dosage at screening,
 
▪ Continuous: age, baseline value for clinic FEV1
 
 
 
○ Interaction: baseline*Visit, treatment*Visit
 
○ Repeated: Visit
 
 
 
• The model will be fit with an unstructured variance-covariance matrix.
 
• The LS mean trough FEV1 and LS mean change from baseline in trough FEV1 will be estimated using the observed marginal distributions of the study population covariates by inclusion of the OM (observed margins) dataset in SAS.
 

Model Checking & Diagnostics

 
• Refer to Appendix 8: Model Checking and Diagnostics for Statistical Analyses.
 

Model Results Presentation

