### Model Specification

- Analyses are based on the treatment policy (de facto) type estimand using the pooled FF doses.
- Baseline definitions are provided in Section 5.2.
- The change from baseline for each endpoint will be analyzed using a Mixed Models Repeated Measures (MMRM) model.
- Terms in the MMRM model
  - Period:
    - SGRQ: Clinic visits Week 12 and 24
    - ACQ-7: Clinic visits at Week 4, 12 and 24
    - E-RS: Weeks 1-4, Weeks 5-8, Weeks 9-12, Weeks 13-16, Weeks 17-20, Weeks 21-24.
  - Covariates:
    - Categorical: treatment group, sex, region, pre-study ICS dosage at screening and period.
    - Continuous: age, baseline value
  - Interaction: baseline\*period, treatment\*period
    - Repeated: period
  - All 6-arm data are included in the model.
  - LSMESTIMATE statement will be used with the treatment code as specified Section 7.
  - For the E-RS endpoint, the average treatment effect over the 24-week treatment period will also be obtained from the model and presented in the analysis output.
- The model will be fitted with an unstructured variance-covariance matrix.
- The OM option in SAS will be used to derive the LS means based on the distribution of the covariates observed in the data

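### Visit 2 FEV1 and ACQ values are already collected but enter neither the primary FEV1 model nor the confirmatory ACQ-7 model; adding them before unblinding is a free precision gain of uncertain size, not a correction.

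*Protocol*

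**What the plan says.** Protocol 5.3.1 makes two Visit 2 measurements conditions of enrolment: an ACQ-6 score of at least 1.5 and "A best pre-bronchodilator morning (AM) FEV₁ $\geq 30\%$ and $< 90\%$ of the predicted normal value at Visit 2". The Time and Events table (Protocol 7.1) schedules ACQ and clinic spirometry at Visits 1, 2 and 3. SAP 6.2 tabulates Visit 2 spirometry and "ACQ-5, ACQ-6, and ACQ-7 scores at Visit 1, Visit 2, and Visit 3", as description only.

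The models use less. In SAP 7.1.6 the continuous covariates of the primary MMRM are "Continuous: age, baseline value for clinic FEV 1", with a baseline-by-visit interaction. Protocol 9.4.1 takes that baseline from the last acceptable or borderline acceptable reading, "either from Visit 3 pre-dose or from Visit 2 pre-bronchodilator"; SAP 5.2 adds unscheduled assessments between the two visits. In SAP 7.3.5.1 the model for SGRQ, ACQ-7 and E-RS lists "Continuous: age, baseline value", and SAP 5.2 fixes the ACQ baseline at the randomization visit. Neither model has a separate Visit 2 term, and no reason is given.

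Protocol 9.4 leaves room for further covariates, and SAP 2.1 used that room to add region to all models.

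**The concern.** One FEV1 session, or one ACQ score with a one-week recall, mixes the subject's underlying level with variation specific to that visit. A second pre-randomization reading can explain part of the Week 24 outcome that a single reading cannot. Because it precedes randomization, adjusting for it cannot bias the treatment comparison, even though Visit 2 follows FSC and Visit 3 follows FF/VI.

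Precision matters because of the testing hierarchy (SAP 5.6). Both UMEC 62.5 mcg FEV1 comparisons must succeed before any other test. ACQ-7 at Level 4 is the last step before the 31.25 mcg dose, and at Level 8 it precedes E-RS. A wider standard error than necessary at these steps lowers the chance of passing them and widens the reported intervals.

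**Working it through.** **Inputs from Protocol 9.2.1.** The SD of change "is estimated to be 400 mL based on previous asthma studies". With 337 evaluable per arm, the trial "should provide 90% power, assuming a difference of 100 mL", "based on a two sample t-test with a two sided significance level of 0.05" per comparison.

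**Reproducing the stated figure.** Noncentral t power with n = 337 per arm, difference 100 mL, SD 400 mL: 0.900. This agrees with the protocol. The two Level 1 comparisons share no arm, so with independent arms the chance that both succeed is 0.900² ≈ 0.81.

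**Formula for a second baseline.** Let r3 and r2 be the correlations of the Visit 3 and Visit 2 values with Week 24, and r23 the correlation between the two visits. Residual variance with both values, divided by residual variance with Visit 3 alone, is

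R = 1 − (r2 − r3·r23)² / [(1 − r23²)(1 − r3²)].

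If all three equal r, this becomes R = (1 + 2r)/(1 + r)². It treats the MMRM at Week 24 as an ANCOVA and leaves out age, sex, region and ICS dosage, so the correlations are best read as those remaining after these covariates. The documents give none of them; every value below is an assumption.

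**FEV1**

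| Assumption | r3 | r2 | r23 | R | Variance saved |
|---|---|---|---|---|---|
| Exchangeable | 0.90 | 0.90 | 0.90 | 0.776 | 22% |
| Exchangeable | 0.80 | 0.80 | 0.80 | 0.802 | 20% |
| Modest decay | 0.85 | 0.84 | 0.90 | 0.893 | 11% |
| Modest decay | 0.85 | 0.82 | 0.90 | 0.943 | 6% |
| Modest decay | 0.85 | 0.80 | 0.90 | 0.977 | 2% |
| Purely serial | 0.85 | 0.765 | 0.90 | 1.000 | 0% |

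In the last row r2 = 0.85 × 0.90 = 0.765, so Visit 2 carries nothing that Visit 3 does not.

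**ACQ-7.** Equal correlations of 0.4, 0.5, 0.6 and 0.7 give R = 0.918, 0.889, 0.859 and 0.830, a saving of 8-17%. With decay, (r3, r2, r23) = (0.50, 0.40, 0.65) gives R = 0.987 and (0.60, 0.50, 0.70) gives R = 0.980, a saving of 1.3% and 2.0%.

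**Range restriction.** The entry limits truncate Visit 2 values. In a simulation with illustrative truncation, exchangeable correlations of 0.5 to 0.9 still saved about 7-21%.

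**Where power starts.** Two readings of the 400 mL are possible.

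- If it is already the residual SD after adjusting for one baseline, power per FEV1 comparison rises from 0.900 to 0.906-0.929 across the modest-decay rows, and to at most 0.957 at R = 0.776.
- If it is the SD of raw change, as the protocol words it, adjusting for one baseline with equal variances multiplies the SD by √[(1 + r)/2]. For r = 0.80 that is 400 × √0.90 = 379 mL and power 0.927; for r = 0.90 it is 400 × √0.95 = 390 mL and power 0.914. The second baseline then takes power to about 0.97.

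SAP 5.4 also records 766 + 643 + 399 + 631 = 2439 randomized. With 10% missing, that is about 365 per arm (2439/6 × 0.9 = 365.9). The unadjusted t-test then has power 0.92, and one-baseline adjustment at r = 0.80-0.90 gives 0.93-0.94.

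**The case against.** The strongest reply is that nothing in the plan is wrong. SAP 5.5.1 justifies each covariate of the primary model, baseline adjustment is standard, and neither the validity of the tests nor the sample size depends on a Visit 2 term. That stands in full.

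Visits 2 and 3 are also not replicates. Visit 2 follows twice-daily FSC and Visit 3 once-daily FF/VI; Protocol 4.4 treats stabilization as the baseline collection period; and the Visit 2 values are truncated by entry limits that are not reapplied at Visit 3 (Protocol 5.4). All of this moves the likely gain away from the exchangeable case and towards the smaller figures. It does not introduce bias.

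A reader might infer more than the documents support, in three ways:

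- **That FEV1 is adjusted only for Visit 3, and that every randomized subject has a separate Visit 2 value to add.** The baseline rule allows Visit 2 or an unscheduled reading, and where the baseline is already Visit 2 the extra term adds nothing. Availability is by criterion; SAP 6.1 plans summaries of entry deviations, and the ITT definition does not remove those subjects.
- **That about a fifth of the variance is being given away.** This needs exchangeable visits, which no document supports.
- **That Level 1 success would rise from 0.81 to about 0.92.** The 0.81 belongs to an unadjusted t-test at 337 per arm, not to the planned model at the enrolment recorded in the SAP.

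Finally, the change does nothing for exacerbations (Level 2) or SGRQ (Level 3), both of which precede ACQ-7, and the documents state no power for ACQ-7. Its step cannot be shown to be weak.

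**Conclusion.** The point holds as an efficiency improvement. The Visit 2 FEV1 and ACQ values are collected by design and tabulated, and then left out of the two models where they could sharpen the estimate. The planned analyses remain valid.

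The size cannot be derived from the documents. Under assumed correlations the FEV1 residual variance falls by nil to about 22%, with about 2-11% under modest decay. The ACQ-7 saving may be only 1-2% if correlation decays. The planned adjusted FEV1 analysis probably starts above 90% power per comparison, so there is less to gain than a calculation from 90% suggests. The case rests on the low cost and the absence of bias, not on a large expected gain.

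**What to change.** Before unblinding:

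- **SAP 7.1.6:** add Visit 2 pre-bronchodilator clinic FEV1 as a continuous covariate, with its interaction with visit, beside the existing baseline terms. Carry the same terms into the imputation model, and the Visit 2 covariate into the Week 24 ANCOVA of the missing-data sensitivity analyses.
- **SAP 7.3.5.1:** add the Visit 2 ACQ-7 score and its interaction with period to the ACQ-7 model only.
- **Rules:** if the Visit 2 value is missing, use the baseline value in the Visit 2 term. If the baseline is itself the Visit 2 value, use that value in both terms.
- **SAP 2.1:** list the change with its reason.

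The endpoint, baseline definition, estimand and testing hierarchy stay as they are. SAP 1.1 places final analysis decisions by source data lock on treatment-blinded data, so the sponsor could first estimate the three correlations from pooled blinded data.

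The cost is SAP wording, some programming and a few degrees of freedom, which is negligible at this sample size. No new data are needed.
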